7.1 Post-Operative Sensitivity

To evaluate the immediate post-operative sensitivity, patients will be contacted by telephone once a week after the initial appointment for four weeks or until the restoration is reported asymptomatic. A criterion-referenced rating scale will be used to measure sensitivity. The phone interview will be used as a follow-up procedure to minimize recall loss as the patient is not required to return to the clinic. During the phone interview a criterion-referenced rating will be made of functional tooth sensitivity using the following scale. Patients will only be asked to return for an evaluation if they are having continued discomfort or any indication of premature occlusal contact.

Sensitivity Criteria:

- 1= No sensitivity is experienced at anytime
- 2= Slight sensitivity is experienced occasionally but it is not uncomfortable
- 3= Moderate sensitivity is experienced occasionally, and it is noticeably uncomfortable
- 4= Severe discomfort is noted routinely with cold or pressure stimulation

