Chairside CAD/CAM restorations are generally delivered with adhesive resin cements. The cement may or not require pre-treatment of the tooth by etching or a bonding agent. This creates potential confusion for a clinician as to what the optimal material selection and treatment process should be. A new adhesive resin cement (Suglue 3/3M) is the latest generation of dual cured resin cements from 3M with the innovation to use different tooth pre-treatment options, self-etch, selective enamel etch, or total etch depending on the type of restoration. This simplifies the selection process for delivery of restorations by minimizing the amount of different materials required.

This investigation will be a longitudinal clinical trial to study the long-term clinical performance of a new adhesive resin cement for chairside CAD/CAM restorations. Lithium disilicate chairside CAD/CAM onlays (IPS emaxCAD/Ivoclar) will be adhesively bonded using a selective enamel etch technique with a new generation universal adhesive based on Scotchbond Universal Adhesive (3M) and a new generation resin adhesive cement based on RelyX Ultimate (3M). Full contour zirconia crowns (3M Chairside Zirconia/3M) will be cemented using a self-adhesive technique with the new generation adhesive cement. All restorations may be followed up to five years of service.

5 Specific Aims

The specific aims of this project are:

1. Evaluate the short-term post-operative sensitivity associated with a self-etching resin cement for adhesive luting of chairside zirconia crowns.
2. Evaluate the short-term post-operative sensitivity associated with the adhesive luting technique for ceramic onlays using a selective enamel etch technique and a universal adhesive and dual cure resin cement.
3. Evaluate the longitudinal clinical performance of lithium disilicate ceramic onlays and full contour zirconia crowns for up to five years of clinical service, for a minimum of 3 years. The onlays and crowns will be evaluated with FDI criteria (Hickel et al., 2007 and 2010) for esthetic properties include surface luster, surface staining, margin staining, color match and translucency; functional properties include anatomical form, material fracture, retention, margin adaptation, occlusal contour and wear, and proximal contact and contour; and biological properties include post-operative sensitivity, recurrence of caries, erosion, abfraction as well as gingival index, and plaque index.

6 Research Plan: Methods and Materials

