6.3 Study Size

There will be 40 zirconia crowns and 40 ceramic onlays placed. The sample size is according to the international standard represented by the criteria of the American Dental Association (ADA, Council on Scientific Affairs: Acceptance Program Guidelines "Restorative Materials", March 1996). 60 patients will be enrolled in the study.

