7.2 Clinical Evaluation

Two independent evaluators will examine all restorations in the study. Clinical evaluations will be made at baseline, six months, one year, two years and three years. If feasible, subjects will return for additional follow-up visits at four and five years. Evaluation criteria are based on FDI criteria (Hickel et al., 2007 and 2010) for esthetic properties include surface luster, surface staining, margin staining, color match and translucency; functional properties include anatomical form, material fracture, retention, margin adaptation, occlusal contour and wear, and proximal contact and contour; and biological properties include post-operative sensitivity, caries, gingival index, and plaque index (see Appendix for FDI criteria description). Disagreements in evaluations will be discussed between the evaluators and a consensus judgment will be reached and recorded for every criteria.

Intraoral digital color pictures at a 1:1.5 magnification will be taken to document pre-operative, cavity preparation, and post-operative conditions. Facial and occlusal views of the tooth will be documented for both the pre-operative and post-operative conditions.

A post-cementation quadrant digital scan will be made of each test restoration using the OmniCam. Digital files will be recorded at the baseline, 6 months, 1 year, 2 year and 3 year. Optionally also at 4- and 5-year recall visits. Bite-wing radiographs and periapical radiographs of each test tooth will be available preoperatively and at the three-year recall for routine, standard of care monitoring of the restorations.

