In case of occurrence of any Adverse Event or Adverse Device Effect the appropriate form provided by 3M has to be filled in by the investigator. In case of any near incident or any event that could lead or led to any medical hazard for the investigator (user) of the investigational device the Incident/Near Incident form provided by the sponsor has to be filled in by the investigator.

Any adverse reactions to the treatment provided as part of the study will be fully investigated and recorded on the Adverse Event/Adverse Device Effect form (See Appendix), including details of the appropriate clinical action taken. An adverse event is defined as any unintended adverse experience associated with the study materials or study procedures that results in an unplanned medical assessment or treatment or changes the risk to subjects.

Restoration Failures

If a crown or onlay fails during the term of the study, the investigator will provide complete information on the manner of the failure and the proposed resolution to the study contact person at 3M. Failures associated with the bonding agent, cement, crowns and onlays that may be expected in this study include:

- loosening or complete loss of the crown or onlay

- fracture and/or chipping of the crown or onlay
- surface roughening or discoloration of the crown or onlay

Upon a determination that the crown or onlay failure did not result from other identifiable causes, and with 3M's prior approval, the Institution will make arrangements to replace the crown or onlay or carry out appropriate alternative treatment (i.e. replacement with a fixed or removable partial denture) at 3M's expense. 3M will not be responsible for any expenses incurred without its prior approval. If a crown or onlay fails after the term of the study, 3M will not be responsible for any costs incurred in its repair or replacement. 3M will have no responsibility for any other treatment a patient may receive during the term of the study or after the study has ended.

Monitoring

Monitoring visits will take place at the study center. During these visits, questions on the study conduct will be discussed and the study documentation will be reviewed. The study monitor will check whether the Clinical Investigation Plan was followed and whether the investigational device was applied according to the Instructions for use. The monitor will verify if appropriate patient consent is available for each patient and that it was included before enrolment.

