Furthermore he/she will check the availability, completeness, logicalness, accuracy and legibility of certain study documents, the CRFs and the Adverse Event/Incident forms. The occurrence of any new Adverse Event/Adverse Device Effect/(near) incident will be reported in the monitoring report and copies of the forms will be collected. Certain data in the CRFs will be verified with source documents (patient files).

The study will be monitored at appropriate intervals by the study monitor, or his/her designee, by means of visits to the study site to evaluate study data and any photographs. Study monitoring visits will involve review of the study status and any issues pertaining to it. All Informed Consent forms, HIPAA forms will be reviewed for signatures; all CRF's will be reviewed for completeness of data entry and that the study protocol is being followed; the subjects'

profiles will be checked to ensure they meet the inclusion and exclusion criteria. Materials will be checked for adequate storage and sufficient quantity to meet the study needs.

Data collection and Data corrections

During monitoring, CRFs will be checked for accuracy, legibility, logicalness and completeness, that all patients have given informed consent, meet selection criteria, and have had treatments randomly allocate in accordance with the study protocol. Resulting changes in the data will be initialized and dated by the person who changed them. If all open questions could be cleared with the investigator, copies of the signed Adverse Event/Incident forms will be provided for the Study Monitor's file. Data entry will be done by [REDACTED], Research Clinic Coordinator of the Cariology, Restorative Sciences Clinical Research Unit.

8 Statistical Analysis

In general, all analyses will be conducted separately by type of restoration; onlay or crown. Means and standard deviations were calculated for all clinical measurements and assessments. Categorical variables were summarized in frequency distributions.

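### Section 7.1: on its natural reading, weekly sensitivity calls stop at the first asymptomatic report, so onset after that call is not systematically captured for Aims 1 and 2

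*Combined protocol and SAP*

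**What the plan says.** Aim 1 in Section 5 reads "Evaluate the short-term post-operative sensitivity associated with a self-etching resin cement for adhesive luting of chairside zirconia crowns"; Aim 2 is the counterpart for the ceramic onlays. The scheduled measurement behind both aims is the phone follow-up in Section 7.1, under which "patients will be contacted by telephone once a week after the initial appointment for four weeks or until the restoration is reported asymptomatic". Each interview yields a score from 1 to 4, and score 1 is worded "No sensitivity is experienced at anytime". Clinic contact in this period is by exception: "Patients will only be asked to return for an evaluation if they are having continued discomfort or any indication of premature occlusal contact".

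Section 7.1 does not say whether the earlier or the later of the two end points governs. It does not tie asymptomatic to a score, and it does not restart calls if symptoms appear later.

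After the calls, the next scheduled assessment is at six months (Section 7.2: "Clinical evaluations will be made at baseline, six months, one year, two years and three years"). On numbers, Section 6.3 states "There will be 40 zirconia crowns and 40 ceramic onlays placed", in 60 patients, and Section 6.1 allows at most two restorations per patient.

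Section 8 names post-operative sensitivity only as an FDI item, compared with baseline at each recall. The phone scores could fall only under its general descriptive sentences, such as "Categorical variables were summarized in frequency distributions". These name no target measure and no denominator for weeks without a call.

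**The concern.** A stopping rule that depends on the outcome decides which later outcomes can be seen. If a tooth leaves phone follow-up once it is reported free of symptoms, the later weeks contain ratings only for teeth that were already sensitive. A tooth that is comfortable in week 1 and sensitive in week 3 then looks the same in the phone data as one that was never sensitive.

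Aims 1 and 2 are two of the trial's three specific aims. Ratings not made in the first month cannot be recovered afterwards, and the collected data cannot show how many episodes were lost. The plan also does not say which summary of the calls answers the aims, so a reader could take a first-call figure for a four-week figure.

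**Working it through.** The documents give no sensitivity rate and no calculation for Aims 1 and 2, so there is no planned figure to reproduce. The check is a logical one, followed by an illustration on assumed rates.

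**Inputs from the documents.** Up to four weekly calls and scores 1 to 4 (Section 7.1); 40 restorations per type and 60 patients (Section 6.3); at most two restorations per patient (Section 6.1).

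**Step 1: the identity.** Take whichever-first, with asymptomatic meaning score 1. A second call is made only if the first scored 2 or more. If the first scored 1, nothing more is recorded. So a recorded score of 2 or more at any time occurs exactly when the first completed call scored 2 or more.

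**Step 2: check over all paths.** Four scores over four weeks give 4^4 = 256 possible paths. These are counts of paths, not probabilities.

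- Recorded any score of 2 or more equals week-1 status in 256 of 256 paths. With missed calls, it equals the first completed call in every pattern (256 × 15 = 3,840 of 3,840).
- Onset after a week-1 score of 1 goes unrated in 4^3 − 1 = 63 paths.
- Return after resolution goes unrated in 3 × 15 + 9 × 3 = 45 + 27 = 72 paths.
- The identity also holds if asymptomatic means score 1 or 2 (no mismatches).
- It does not hold for a score of 3 or more, because teeth scored 2 or more stay in follow-up and can worsen. Recorded any-time status differs from week 1 in 32 + 8 + 2 = 42 paths and from true any-time status in 56 + 12 + 2 = 70.

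If whichever-later applies, all four calls are always made and nothing is lost.

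**Step 3: size, on assumed rates.** Let p be the proportion with score 2 or more at week 1, and h the weekly onset in weeks 2 to 4 among teeth not yet sensitive. True any-time proportion = 1 − (1 − p)(1 − h)^3. Teeth not recorded = 40 × (true − p).

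| p | h | True any-time | Recorded | Teeth missed of 40 |
|---|---|---|---|---|
| 10% | 0 | 10.0% | 10% | 0 |
| 10% | 1% | 12.7% | 10% | 1.1 |
| 10% | 2.5% | 16.6% | 10% | 2.6 |
| 10% | 5% | 22.8% | 10% | 5.1 |
| 20% | 0 | 20.0% | 20% | 0 |
| 20% | 1% | 22.4% | 20% | 1.0 |
| 20% | 2.5% | 25.9% | 20% | 2.3 |
| 20% | 5% | 31.4% | 20% | 4.6 |

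For example, 1 − 0.90 × 0.95^3 = 1 − 0.90 × 0.857375 = 0.2284. The exact 95% intervals for the recorded figures are 2.8% to 23.7% (4/40) and 9.1% to 35.6% (8/40), so every value in the table lies inside its interval.

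**Step 4: why the denominator must be stated.** Assume 8 of 40 teeth are sensitive at week 1 and half resolve each week. Calls made are 40 + 8 + 4 + 2 = 54 of 160 possible. Percent sensitive among teeth called is 8/40, 4/8, 2/4, 1/2 = 20, 50, 50, 50. Over all 40 it is 20, 10, 5, 2.5. The first series is selected on symptoms. The second treats every uncalled tooth as symptom-free, which is exactly what is not known.

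**The case against.** The strongest reply is that the measure at risk is not in the plan. No section promises a figure for any sensitivity over weeks 1 to 4, and Section 7.1 describes its purpose as immediate sensitivity. Calling until symptoms clear suits that purpose: it gives first-call status and time to first asymptomatic report. This stands. A reader might infer that the trial will report a downward-biased four-week incidence, but the documents do not support that, because they plan no such figure.

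A reader might also infer that later episodes are never recorded. That too goes beyond the documents:

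- If all 60 patients receive at least one of the 80 restorations, 80 − 60 = 20 patients have two, together 40 of the 80. A patient still being called about one tooth may be re-rated on the other; nothing excludes it.
- Patients with continued discomfort may return to the clinic.
- An adverse event is recorded if it "results in an unplanned medical assessment or treatment or changes the risk to subjects", although a score of 2, defined as not uncomfortable, would seldom qualify.
- The FDI sensitivity item at six months has a grade for minor, time-limited hypersensitivity, but it gives neither the week nor the phone grade.

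These routes catch some episodes, not all, and not on a schedule.

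The wording of score 1 is also unclear. If it covers the whole period since placement, a tooth once sensitive could never score 1, and the 72 return paths disappear. The 63 late-onset paths remain.

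Finally, the onset rates above are assumptions and the range includes zero. The call rule may be clarified in material not available here: Section 6.4 has a heading but no text in this copy, and the case report form manual is not included.

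**Conclusion.** The point holds in a limited form. On the natural whichever-first reading, with asymptomatic meaning score 1, the calls measure sensitivity at the first completed call and how long it lasts. Onset after a first score of 1 is not systematically captured before six months. The loss is zero without late onset and about 1 to 5 of 40 teeth per type if 1% to 5% of teeth not yet sensitive become so each week. These rates are assumed; the documents give none. The loss is modest beside sampling error at n = 40, but it can run only one way and cannot be estimated from the data collected.

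It would be tempting to conclude that the trial's main result is compromised. It is not: the primary analysis is restoration survival, and Section 8 analyses each restoration type separately, so no between-type comparison depends on these calls. This is a cheap improvement in measurement and reporting, not a demonstrated estimation error.

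**What to change.** **Section 7.1.** Rate every restoration by phone at each of weeks 1, 2, 3 and 4 whatever the earlier answer, with each rating covering the period since the last call. This removes both the two readings of the stopping rule and the unclear time span of score 1.

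**Section 8, by restoration type.**

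- For each week, report the number and percent with score 2 or more and with score 3 or more among restorations rated that week, with the number not rated shown beside 40.
- For any time in weeks 1 to 4, report the percent among restorations with all four ratings. Add bounds over all restorations placed, counting unrated teeth first as not sensitive and then as sensitive. A tooth already scored at or above the threshold counts as sensitive in both.
- Do not apply last observation carried forward to these scores, since a carried-forward 1 assumes no late onset.
- Give 95% confidence intervals that allow for two restorations in one patient.

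**Cost.** Protocol and SAP wording, plus at most 80 × 3 = 240 extra short calls by the existing coordinator, fewer where one call covers a patient's two teeth. No extra visits.

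**If the calls are not extended.** State that the target is sensitivity at the first completed call and time to first asymptomatic report, define asymptomatic by score, show restorations with no completed call separately, and make no any-time claim. This costs wording only.

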7.2 Clinical Evaluation

Two independent evaluators will examine all restorations in the study. Clinical evaluations will be made at baseline, six months, one year, two years and three years. If feasible, subjects will return for additional follow-up visits at four and five years. Evaluation criteria are based on FDI criteria (Hickel et al., 2007 and 2010) for esthetic properties include surface luster, surface staining, margin staining, color match and translucency; functional properties include anatomical form, material fracture, retention, margin adaptation, occlusal contour and wear, and proximal contact and contour; and biological properties include post-operative sensitivity, caries, gingival index, and plaque index (see Appendix for FDI criteria description). Disagreements in evaluations will be discussed between the evaluators and a consensus judgment will be reached and recorded for every criteria.

Intraoral digital color pictures at a 1:1.5 magnification will be taken to document pre-operative, cavity preparation, and post-operative conditions. Facial and occlusal views of the tooth will be documented for both the pre-operative and post-operative conditions.

A post-cementation quadrant digital scan will be made of each test restoration using the OmniCam. Digital files will be recorded at the baseline, 6 months, 1 year, 2 year and 3 year. Optionally also at 4- and 5-year recall visits. Bite-wing radiographs and periapical radiographs of each test tooth will be available preoperatively and at the three-year recall for routine, standard of care monitoring of the restorations.

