6.1 Subjects

The patient population will be selected from current patients under clinical treatment at the University of Michigan Dental Clinics. Patients need to volunteer for the study and must sign the informed consent. Patients will be over 18 years of age, of either gender, and of any ethnic background. Each patient should have at least one carious lesion or defective restoration to be restored on a maxillary or mandibular premolar or molar. Each lesion or defective restoration should exhibit sufficient size to extend at least one-half the intercuspal width of the tooth requiring an onlay or full crown restoration. The onlays may contain between one and three cusps on the selected tooth as long as an occlusal margin will be present. All teeth will test vital and be asymptomatic at the beginning of treatment. No more than two restorations will be placed per patient. If a patient presents with more than two acceptable teeth for the study, molar teeth will be included prior to premolar teeth. Exclusion criteria will include:

Devital or sensitive teeth

Teeth diagnosed with symptoms of incomplete tooth fracture

Teeth with prior endodontic treatment of any kind

Teeth with a history of direct or indirect pulp capping procedures

Subjects with uncontrolled bruxism or parafunctional habits

Subject has known allergies to any product used during this study

Subject will not be available for the study duration of 5 years

Subjects with significant untreated dental disease to include periodontitis and rampant caries

Pregnant or lactating women

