There will be two datasets analyzed at each recall period; (1) one dataset consisting of subjects who were enrolled up to and including that recall period, and (2) one dataset consisting of all subjects with baseline data. In the second dataset (2) primary and secondary outcome variables which are missing will be imputed using the method of last observation carried forward (LOCF), wherein the last observed values for that variable will be carried forward to all remaining timepoints.

The primary analysis for this study will be the percent of intact/surviving restorations from baseline to the end of each recall period. This will be estimated using the Kaplan-Meier method, there will be no direct comparisons within this analysis. The median survival time of a restoration will be presented alongside survival curves.

The secondary analyses for this study will relate to the FDI criteria for esthetic properties including surface luster, surface staining, margin staining, color match and translucency; functional properties including anatomical form, material fracture, retention,

margin adaptation, occlusal contour and wear, and proximal contact and contour; and biological properties including post-operative sensitivity, caries, gingival index, and plaque index (see Appendix for FDI criteria description). The FDI criteria will be assessed at each recall period versus their respective baseline scores for a particular restoration within a particular subject. FDI criteria which are measured in an ordinal-discrete manner will be assessed using the Wilcoxon-signed rank test. Criteria which are measured continuously such as PI and GI will be assessed using the student's t-test, in the event that the PI and GI scores do not appear to be Normally distributed this assessment will shift to be done using the Wilcoxon-signed rank test.

A two-sided alpha of 0.05 will be used for all comparisons. There will be no adjustments made for multiplicity.

All statistical analyses will be performed e.g. using SAS version 9.4 or above (SAS Institute, Cary, NC).

9 Project Time Line

The recruitment of patients and clinical placement of restorations will begin immediately upon approval and funding of the project. It is anticipated to take 9-12 months to recruit and place the restorations required for the study.

Protocol Amendments and Discontinuing the Study

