After approval of the study protocol, any changes to the content of the study documentation must be described in an Amendment Form and be approved by the PI, 3M, and the reviewing IRB prior to implementation. Any decision as to whether to prematurely stop the study will be taken jointly by the PI, 3M, and the IRB. Where early termination of the study occurs, subjects will receive appropriate follow up dental treatment.

10 Equipment

A CEREC system including a CEREC OmniCam and PrimeScan, MCX mill, Programmat oven, and SpeedFire oven is available at the University of Michigan for use during the study. All other instrumentation required for placement and clinical evaluation of the restorations is available through the Research Clinic of the Department of Cariology, Restorative Sciences, and

Endodontics at the University of Michigan School of Dentistry. Additional measurement instrumentation to include measuring microscopes, scanning electron microscope, computer analysis, and intraoral imaging equipment is available within the School of Dentistry.

11 Facilities

The Graduate General Dentistry Clinic maintains a two chair Clinical Research Unit for clinical research within the department. A full time Clinical Research Coordinator is dedicated to the Clinical Research Unit as well. She will coordinate and schedule all patient appointments, maintain recall schedules, and collate data collected. A Certified Dental Assistant will also provide clinical support as well. Additional dental materials and instruments as well as personnel support will be provided by the Graduate General Dentistry Clinic as needed.

12 Additional Sponsorships:

No other sponsorships are presently available or will be applied to this project.

In the event that study restorations should fail and require replacement, patients may elect to have a laboratory-fabricated restoration placed instead of another test restoration. [REDACTED]

[REDACTED]

[REDACTED]

[REDACTED]

13 References

[figure not shown]
[figure not shown]
[figure not shown]
[figure not shown]

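### Restoration survival is scheduled to be assessed only at attended recalls, and LOCF counts a missed restoration last seen intact as surviving; a status check at each missed recall would reduce this bias

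*Combined protocol and SAP*

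**What the plan says.** **Outcome.** Section 8 defines the primary analysis: "The primary analysis for this study will be the percent of intact/surviving restorations from baseline to the end of each recall period". It is estimated by Kaplan-Meier for each restoration type separately, with no comparison. Section 8 does not define the event that ends survival.

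**Scheduled assessment.** Section 7.2: "Clinical evaluations will be made at baseline, six months, one year, two years and three years". Years 4 and 5 follow if feasible. Two evaluators examine each restoration.

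**Failures between visits.** Section 7.3, under Restoration Failures, has the investigator report any failure during the study to the sponsor. It lists loosening or loss, fracture or chipping, and surface roughening or discoloration as failures to expect.

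**Missing outcomes.** Section 8 plans two datasets at each recall. One holds subjects enrolled up to that recall, with no imputation stated. The other holds all subjects with baseline data, with LOCF for missing primary and secondary outcomes. Neither is named as primary.

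**Telephone contact.** Section 7.1 plans weekly calls for at most four weeks, recording sensitivity only, and gives the reason: "The phone interview will be used as a follow-up procedure to minimize recall loss as the patient is not required to return to the clinic". The caller is not named.

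**Staff and size.** Section 11: "A full time Clinical Research Coordinator is dedicated to the Clinical Research Unit as well"; this person also keeps the recall calendar. Section 6.3: "There will be 40 zirconia crowns and 40 ceramic onlays placed" and "60 patients will be enrolled in the study".

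**The concern.** Neither section 7.2 nor section 8 says how the status of a restoration is to be learned when its patient misses a recall. The failure report in section 7.3 is passive. It works when a patient comes back or the site hears of the problem; it does not reveal a failure treated elsewhere, and it never confirms that a silent patient's restoration is still in place.

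In the all-baseline dataset, LOCF then turns an unknown status into survival at every remaining time point. For a one-way event such as failure, the error can only raise the estimate. The same protocol already accepts patient reports by telephone where attendance would otherwise cost data. Participants are also current patients of the University's dental clinics (section 6.1), so a record check is plausible. Status that was never collected cannot be recovered at the analysis stage.

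**Working it through.** **1. The plan's own figure.** 40 + 40 = 80 restorations in 60 patients. Section 6.1 says "No more than two restorations will be placed per patient", so capacity is 60 × 2 = 120 and 80 is feasible. If all 60 are treated, 80 − 60 = 20 patients have two restorations. The basis given is "The sample size is according to the international standard represented by the criteria of the American Dental Association". No precision, power or dropout input is stated, so the size cannot be re-derived and contains no attrition figure to borrow.

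**2. Inputs.** From the documents: n = 40 per type. Assumed, because the documents are silent:
- d, share missing at a recall: 10%, 20% or 30% (4, 8 or 12 of 40)
- g, failure proportion among those seen: 5%
- f, failure proportion among the missing that has not reached the site: 5%, 10% or 20%
- r, share of the missing reached
- s, share of their failures that a call or record reveals

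The calculation uses proportions at a single recall. A full Kaplan-Meier analysis would also use earlier visits.

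**3. Bias before any call.**
- True survival = (1 − d)(1 − g) + d(1 − f)
- LOCF, all missing last seen intact = (1 − d)(1 − g) + d, so bias = d × f
- Censoring the missing = 1 − g, so bias = d × (f − g)

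Example, d = 0.20 and f = 0.10: true 0.80 × 0.95 + 0.20 × 0.90 = 94.0%; LOCF 0.76 + 0.20 = 96.0%; censoring 95.0%.

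| d | f | LOCF bias (points) | Censoring bias (points) |
|---|---|---|---|
| 10% | 5% / 10% / 20% | 0.5 / 1.0 / 2.0 | 0 / 0.5 / 1.5 |
| 20% | 5% / 10% / 20% | 1.0 / 2.0 / 4.0 | 0 / 1.0 / 3.0 |
| 30% | 5% / 10% / 20% | 1.5 / 3.0 / 6.0 | 0 / 1.5 / 4.5 |

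For scale, one restoration is 1/40 = 2.5 points. At d = 20%, 8 are missing and the hidden failures number 8 × 0.05 = 0.4 to 8 × 0.20 = 1.6.

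**4. What a call adds.** It reveals a fraction r × s of hidden failures: 0.5 × 0.6 = 30%, 0.7 × 0.8 = 56%, 0.9 × 1 = 90%. If everyone else stays under LOCF, the remaining bias is d × f × (1 − r × s). In the example, that is 1.4, 0.9 and 0.2 points.

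If those not reached are censored instead, estimated failure = [(1 − d)g + d × r × s × f] / [(1 − d) + d × r]:
- r = 0.5, s = 0.6: (0.040 + 0.006)/0.90 = 5.11%; survival 94.9%, bias +0.9
- r = 0.7, s = 0.8: (0.040 + 0.0112)/0.94 = 5.45%; survival 94.6%, bias +0.6
- r = 0.9, s = 1: (0.040 + 0.018)/0.98 = 5.92%; survival 94.1%, bias +0.1

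**5. When a call can mislead.** If the missing fail no more often than the seen (f = g = 5%), censoring alone is unbiased. A call with r = 0.7 and s = 0.8 gives (0.040 + 0.0056)/0.94 = 4.85%, a bias of about +0.1 point, because undetected defects earn event-free time.

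**6. Extreme bounds.** With 2 observed failures and 4, 6 or 8 of 40 unseen, survival lies between 34/40 = 85%, 32/40 = 80% or 30/40 = 75% and 38/40 = 95%. The lower ends require every unseen restoration to have failed.

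**The case against.** **Failures do have another route.** A reader might infer that status is recorded only at recalls. Section 7.3 contradicts that, and replacement at the sponsor's expense, subject to its approval, gives a patient with a lost restoration a reason to return. This lowers f but leaves silent patients unconfirmed.

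**The telephone precedent is limited.** A reader might infer that the coordinator already makes these calls. Section 7.1 names no caller, the calls end before the first recall at six months, and the stated purpose concerns sensitivity. What stands is that the plan accepts telephone reports in principle and has staff to make them.

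**A call may recover little.** It is tempting to say that it would recover most of the missing outcome data. Nothing in the documents supports this: patients who miss visits may be hard to reach, and the School's record may not show treatment elsewhere. More than half of hidden failures are revealed only if r × s exceeds 0.5.

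**Much of the gain needs no call.** In the example, censoring instead of LOCF halves the bias, from 2.0 to 1.0 points. Kaplan-Meier can do this already, LOCF is specified for one dataset only, and a later attended recall often settles an earlier miss.

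**Reported status is coarse.** A patient cannot grade hairline cracks, small chips, margins or caries. Step 5 shows that the resulting bias is real, though small under those assumptions. This is why the fix needs an event definition and a sensitivity analysis.

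**The visible record is incomplete.** Text in section 6.2 is redacted and consent pages are not available, so a contact procedure may be described there. Sections 7.2 and 8, where it would feed the primary outcome, refer to none.

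**Conclusion.** The point holds as a low-cost improvement. Scheduled assessment of the primary outcome depends on attendance, the other route is passive, and LOCF in the all-baseline dataset credits survival to restorations nobody has checked. The expected overstatement is about 1 to 4 points per type at 20% missing with 5% to 20% hidden failure among the missing. Across 10% to 30% missing it is 0.5 to 6 points. All these rates are assumed.

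Two stronger conclusions do not follow. The 75% to 95% range is an extreme bound, not a likely error. Nor do the documents show that missed recalls go with failure: a patient without complaints may also stay away, and then LOCF happens to be right. Under LOCF the direction of any error is known; its size, and the share that a call would remove, are not.

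**What to change.** **Section 7.2.** For each recall missed up to year 3, existing staff phone the patient and check the School's dental record. They record in place, lost or debonded, grossly fractured, replaced, or tooth extracted, with the date and the source. FDI scores stay missing.

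**Section 8.**
- Define the failure event and state which components may be reported by the patient or taken from a record.
- Enter those events in the Kaplan-Meier analysis at their dates, and otherwise censor at last confirmed status. Do not apply LOCF to the primary outcome.
- Add a sensitivity analysis that censors at the last clinical examination.
- Report how many statuses came from each source.

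**Cost.** A few calls per recall (one covers both restorations of a two-restoration patient), a short script and one eCRF page. Status from a call or record is less exact than an examination and must be flagged by source.
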